#### **4. Inclusion/Exclusion Criteria**

- Inclusion:
  - patients followed in the pain management clinic in the Department of Physical Medicine and Rehabilitation who are followed by [name] and PIs from collaborating sites.
  - patients with a diagnosis of either cervical, thoracic, or lumbar facet or sacroiliac joint pain who have responded to medial branch blocks and are already scheduled for bilateral radiofrequency ablations
  - age greater than 18 years old
  - English speaking
- Exclusion:
  - not previously scheduled for radiofrequency ablation of the cervical, thoracic, or lumbar facets, or sacroiliac joints
  - Recent systemic or local corticosteroids in the last 3 months
  - on anticoagulation
  - have a pacemaker
  - age less than 18 years old
  - non-English speaking

#### **5. Drugs/ Substances/ Devices**

a. The rationale for choosing the drug and dose or for choosing the device to be used.

- Dexamethasone is a well-known anti-inflammatory medication that is often used in transforaminal epidural steroid injections and intra-articular facet injections. The dose of dexamethasone is 4mg/mL, with 1 mL given at each level. PAN is caused by inflammation due to the nature of the procedure. The rationale behind dexamethasone pre-treatment is that the inflammatory response would be blunted and subsequent pain would be reduced or eliminated.

b. Justification and safety information if FDA approved drugs will be administered for non-FDA approved indications or if doses or routes of administration or participant populations are changed.

- Dexamethasone has a well-known safety profile. The medication will be used at doses that are currently used in routine spinal corticosteroid injection procedures. The only difference is that the dose will be given after radiofrequency ablation at each lesion site.
- c. Justification and safety information if non-FDA approved drugs without an IND will be administered.: N/A

## 6. Study Statistics

- a. Primary outcome variable.
  - Presence of post-ablation neuritis at each lesion site
- b. Secondary outcome variables: none
- c. Statistical plan including sample size justification and interim data analysis.
  - A McNemar's Test will be performed to compare the incidence PAN in the placebo and treatment groups
  - As the most important outcome measure is the nominal measure of whether neuropathic pain develops after ablation, we will collect dichotomous data (neuritic vs. no-neuritic pain). We will perform McNemar's Test to test for a difference in proportions across paired samples (each patient providing his/her own control through unilateral injections of steroid and placebo-saline into each side). We will consider a p-value of less than 0.05 as significant.
  - We will collect a total of 732 samples, where each sample is nerve(s) lesioned on one side; i.e. for a patient receiving a two-level ablation bilaterally, the patient will provide a total of two samples (one experimental-steroid, one placebo-saline). Because we will only collect data from patients with bilateral injections, each acting as his/her own control, the total 732 samples will be comprised of 366 participants for each experimental/placebo condition. We plan to enroll 120 patients at Johns Hopkins and 246 from our collaborating sites in order to get total of 366 participants for each experimental/placebo condition.
  - The sample size was derived through a power-analysis calculation using G\*Power Software (ver. 3.1; Heinrich-Heine Universitat). Specifically, an *a priori* test was performed for the McNemar test with a power of 0.8 and significance level of 0.05. Based on available literature (CITE), we determined that baseline incidence of neuropathic pain is 5%, and further determined that a desirable effect size is a minimum of 50% decrease in incidence with steroid injection (overall incidence of 2.5%). With these values, the contingency table showed an odds ratio of 0.487, and the probability of discordant pairs was 0.0725, leading to a total sample size of 732 (actual power 0.82).
- d. Early stopping rules.
  - study will also be terminated if there appears to be greater than expected (>10%) incidence of PAN in the treatment group during interim analyses

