  - The procedure schedule will be sent to [name] (or respective collaborating PIs) and the research team members the night before procedure day with the scheduled patients. Patients in the study will be marked on this schedule.
  - The research team adds the eligible patients to a separate list that is sent to an un-blinded co-investigator with directions on which side to inject dexamethasone or normal saline based on randomization
- e. Justification of why participants will not receive routine care or will have current therapy stopped:
  - Not applicable. All patients in this study will continue to receive routine care, through scheduled ablation procedure and continuation of established medication regimen for pain management.
- f. Justification for inclusion of a placebo or non-treatment group.
  - A placebo group is present to compare the current standard of care and the addition of our intervention and to ensure that any changes are the not the result of the experimental paradigm (i.e. active injection post-lesion).
- g. Definition of treatment failure or participant removal criteria.
  - Treatment failure is defined as the presence of post-ablation neuropathic pain in the period up to 2 months after post-ablation steroid administration.
  - Participant removal criteria:
    - at patient request for removal

- development of immediate onset of weakness or sensory changes post-injection. At that point, the patient will not be given further injections, but data will be used to report an adverse event
- lack of post-procedure follow up
- Any additional procedures that include additional steroid administration

h. Description of what happens to participants receiving therapy when study ends or if a participant's participation in the study ends prematurely.

- Patients will continue with routine care when the study ends or if their participation in the study ends prematurely. They will be continued to be followed at the pain clinic, and if determined to need subsequent radiofrequency ablations after the participation in the study, these will be done routinely without administration of post-ablation dexamethasone or normal saline.

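### Data are limited to patients injected on both sides, so primary events are lost if patients with first-side PAN do not return for the second side

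*Combined protocol and SAP*

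**What the plan says.** Section 6, item c, defines a sample as one treated side. It gets from 732 samples to 366 participants by saying that "we will only collect data from patients with bilateral injections". The only analysis named is paired: "We will perform McNemar's Test to test for a difference in proportions across paired samples". Enrolment is 120 patients at the coordinating centre and 246 elsewhere, "in order to get total of 366 participants for each experimental/placebo condition", and 120 + 246 = 366 leaves no allowance for incomplete pairs.

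Study Procedures, item a, puts the second side at least a week after the first. Section 3 gives a PAN duration of 2 to 6 weeks after lumbar or sacroiliac ablation and an average of 2.6 months after cervical ablation. First-side PAN can therefore be present when the second side is due.

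Study Procedures, item g, lists the ways a patient leaves the study. They include the patient's own request and "lack of post-procedure follow up". No section defines an analysis set, says what happens to the outcome of a patient treated on one side only, or describes the handling of missing data.

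**The concern.** Receiving both injections is known only after randomisation, and after the first-side outcome has had time to appear. A data set defined by it is conditioned on something the primary outcome may affect. If some patients with first-side PAN do not come back, every one of them carries a primary event, so a loss that looks trivial as a dropout percentage takes a much larger share of the events.

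Three things are at stake:

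- the number of discordant pairs, which is all the information McNemar's test uses;
- the reported incidence of PAN, which is the subject of the primary objective;
- the treatment-group PAN rate that the early stopping rule (Section 6, item d) compares with 10%.

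**Working it through.** **Inputs from Section 6, item c.** PAN incidence 5% with saline and 2.5% with dexamethasone; 366 patients; alpha 0.05 with sidedness not stated (two-sided used here).

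**Assumptions.** Half the patients receive saline first. A share q of patients with first-side PAN do not return. The two sides are independent, which is what the plan's own discordance figure implies.

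**1. The plan's figures.** Let b be PAN on the saline side only, c PAN on the dexamethasone side only, and a PAN on both.

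- b = 0.05 × 0.975 = 0.04875
- c = 0.95 × 0.025 = 0.02375
- a = 0.05 × 0.025 = 0.00125
- b + c = 0.0725 and c/b = 0.487, both as stated in the plan
- Expected discordant pairs: 366 × 0.0725 = 26.5

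The stated 732 with power 0.82 reproduces only as 732 pairs, one-sided, with the discordant count fixed at 53 (power 0.822). At the 366 pairs actually planned, exact power is 0.35 two-sided or 0.49 one-sided before any loss. That is a separate and larger problem; it sets the baseline here.

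**2. Restricting to patients treated on both sides.** In a discordant patient the event falls on the first side half the time, so b and c each become (1 − q/2) times their value, and a becomes a(1 − q). The share of patients lost is q(0.05 + 0.025)/2 = 0.0375q.

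At q = 0.4 the share lost is 0.015, or 366 × 0.015 = 5.5 patients:

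- saline incidence: (0.04875 × 0.8 + 0.00125 × 0.6)/0.985 = 0.03975/0.985 = 4.0%
- dexamethasone incidence: (0.02375 × 0.8 + 0.00125 × 0.6)/0.985 = 0.01975/0.985 = 2.0%

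| q | Patients lost | Discordant pairs | Exact two-sided power | Asymptotic two-sided power |
|---|---|---|---|---|
| 0 | 0 | 26.5 | 0.35 | 0.44 |
| 0.2 | 2.7 | 23.9 | 0.31 | 0.41 |
| 0.4 | 5.5 | 21.2 | 0.28 | 0.37 |

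The exact column is the binomial test on discordant pairs. The asymptotic column is the uncorrected McNemar chi-square. Both are averaged over the random number of discordant pairs.

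**3. Odds ratio.** With the same q after either injection, c(1 − q/2)/[b(1 − q/2)] = c/b = 0.487, unchanged. With q = 0.4 after saline PAN and 0.1 after dexamethasone PAN, it is (0.02375 × 0.95)/(0.04875 × 0.8) = 0.58, and exact power is 0.18.

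**4. What an analysis of all treated sides recovers.** A risk difference with variance clustered by patient keeps power at about 0.43 to 0.44 over this range of q. The like-for-like comparator is asymptotic McNemar: 0.41 at q = 0.2 and 0.37 at q = 0.4. The gain is about 0.02 to 0.07. At q = 0 both methods use the same data and there is no gain.

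**5. Correlated sides.** Take an assumed joint probability a = 0.015, so b = 0.035 and c = 0.010, with q = 0.4. First sides are all observed; second sides are missing where the first side had PAN and the patient stopped.

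- Saline, all treated sides: [0.5 × 0.05 + 0.5 × (0.035 + 0.015 × 0.6)]/[0.5 + 0.5 × (1 − 0.4 × 0.025)] = 0.047/0.995 = 4.7%
- Dexamethasone, all treated sides: [0.5 × 0.025 + 0.5 × (0.010 + 0.015 × 0.6)]/[0.5 + 0.5 × (1 − 0.4 × 0.05)] = 0.022/0.990 = 2.2%
- Complete pairs only: (0.035 × 0.8 + 0.015 × 0.6)/0.985 = 3.8% and (0.010 × 0.8 + 0.015 × 0.6)/0.985 = 1.7%

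Using all treated sides reduces the understatement but does not remove it.

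**The case against.** The strongest reply is that the loss is hypothetical. PAN is not a removal criterion, Study Procedures item a has patients with PAN observed or treated, and nothing there cancels the second side. That stands: every value of q is assumed, and the point must be conditional.

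A second reply is that the sentence in Section 6 only explains why 732 samples are 366 people, echoing the eligibility rule that patients be scheduled for bilateral ablation. That is a fair reading, but it does not remove the gap. McNemar's test needs both sides, so a patient treated on one side leaves the only planned analysis either way.

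Three stronger readings are tempting, and the documents do not support them.

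- A reader might infer that patients removed for immediate weakness or sensory change are lost primary events. Item g says of them: "At that point, the patient will not be given further injections, but data will be used to report an adverse event". Section 3 describes PAN as a burning pain where the lesion was made. Nothing shows that an immediate deficit is that outcome, and the data are kept for at least one purpose.
- A reader might infer that the odds ratio is biased toward 1. That needs more stopping after saline PAN than after dexamethasone PAN. Order is randomised and patients and providers are blinded, so the 0.58 in step 3 is speculative.
- A reader might set the all-sides power against exact McNemar and see a large rescue. Most of that gap is the conservatism of the exact test, and it is present with no loss at all.

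The effect is also small beside the shortfall noted in step 1. That too is fair, although a trial starting at 0.35 has little room to lose pairs.

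**Conclusion.** The concern holds in conditional form. As written, the plan limits its data to patients who pass a post-randomisation event that the primary outcome can influence, and it has no rule for anyone else. If a share q of patients with first-side PAN do not return, the trial loses a fraction q/2 of its discordant pairs: a tenth at q = 0.2 and a fifth at q = 0.4, while only 0.75% and 1.5% of patients are lost. Reported incidence is understated in both conditions, and so is the rate the stopping rule watches.

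With equal stopping after either injection, the harm is lost power and understated incidence, not a distorted odds ratio. These sizes rest on the plan's 5% and 2.5%, independent sides, balanced order and an assumed q. The true q is unknown and could be close to zero. The change is worth making because it is cheap, but it is less urgent than the mismatch between pairs and samples in the sample size.

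**What to change.** Replace the sentence in Section 6, item c, with: *PAN will be collected and reported for every randomised patient from the first injection onward, whether or not the second side is treated.* Then:

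- Count these first-side events in the treatment-group rate used by the stopping rule.
- Keep McNemar's test on complete pairs.
- Pre-specify one supporting analysis of all treated sides, with variance clustered by patient. State that it recovers about 0.02 to 0.07 of power like for like over the range examined, and that it reduces but does not fully remove the understatement when the two sides are correlated.
- Report the number of one-sided patients and their reasons for stopping, by injection received.
- Restate the expected number of complete pairs and the power under an assumed loss, instead of counting on 366 of 366. For scale, a 10% loss from any cause leaves 366 × 0.9 = 329 pairs and exact two-sided power of 0.31.

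The cost is a protocol wording change, follow-up of a few one-sided patients through the existing two-week call and scheduled visits, one extra table and one extra analysis. The drawback is a second estimate to report beside McNemar's. No treatment or procedure changes.

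### The 732 in the power calculation counts patient pairs, but the plan spends it as single sides and enrols 366 pairs; power is about 0.35 two-sided (0.49 one-sided), not 0.82

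*Combined protocol and SAP*

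**What the plan says.** The analysis is paired within patient. Each patient receives steroid on one side and saline on the other, and section 6c says "We will perform McNemar's Test to test for a difference in proportions across paired samples". The significance rule is "We will consider a p-value of less than 0.05 as significant", with no mention of one or two sides and no choice between an exact and an asymptotic form of the test.

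The same section describes a G\*Power calculation for the McNemar test with power 0.8 and significance level 0.05. Its inputs are a baseline PAN incidence of 5%, an incidence of 2.5% with steroid, an odds ratio of 0.487 and a discordance probability of 0.0725. The result is "the probability of discordant pairs was 0.0725, leading to a total sample size of 732 (actual power 0.82").

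The plan then defines a sample as whatever is lesioned on one side, so each patient supplies two. It concludes that "the total 732 samples will be comprised of 366 participants for each experimental/placebo condition", and sets recruitment accordingly: "We plan to enroll 120 patients at Johns Hopkins and 246 from our collaborating sites".

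**The concern.** In a McNemar calculation the unit is the pair. The discordance probability is a probability per pair, so the sample size that comes out is a number of pairs. Here one patient is one pair. Reading the output as single sides and dividing by two gives the trial half the information that the calculation requires.

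This is the only power justification for the only primary test. If it is wrong by a factor of two, a real halving of PAN would probably be missed in a two-sided test. A reader who trusts the stated 0.82 would then take the non-significant result as evidence that dexamethasone does not work.

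**Working it through.** **Inputs (all from section 6c).** Saline incidence 0.05; steroid incidence 0.025; level 0.05; target power 0.80; discordance 0.0725; odds ratio 0.487; planned enrolment 120 + 246 = 366 patients.

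**1. The plan's inputs reproduce, as per-pair quantities.** Taking a patient's two sides as independent:
- PAN on the saline side only: 0.05 × 0.975 = 0.04875
- PAN on the steroid side only: 0.025 × 0.95 = 0.02375
- Discordance: 0.04875 + 0.02375 = 0.0725
- Odds ratio: 0.02375 / 0.04875 = 0.487

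**2. The plan's output reproduces if N counts pairs and the test is one-sided.** Given d discordant pairs, the number with PAN on the steroid side is Binomial(d, 0.5) under the null and Binomial(d, 0.02375/0.0725) under the alternative.
- The smallest d with one-sided exact power of at least 0.80 is 53. The test rejects at 20 or fewer, and its power is 0.8215. This is the stated 0.82.
- Pairs needed to expect 53 discordant: 53 / 0.0725 = 731.03, rounded up to 732. This is the stated 732.
- Two-sided, the same method needs d = 65 (power 0.803), and 65 / 0.0725 = 896.6, rounded up to 897 pairs.

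**3. Power of the trial as planned.** With 366 pairs the expected number of discordant pairs is 366 × 0.0725 = 26.5. The exact figures below average over the number of discordant pairs, taken as Binomial(N, 0.0725).

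| Pairs | Test form | One-sided 0.05 | Two-sided 0.05 |
|---|---|---|---|
| 366 | Exact | 0.49 | 0.35 |
| 366 | Normal approximation | 0.55 | 0.43 |
| 366 | Uncorrected chi-square | 0.56 | 0.44 |
| 732 | Exact | 0.78 | 0.68 |
| 732 | Normal approximation | 0.81 | 0.71 |

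The exact figure for 732 pairs one-sided is 0.78, not 0.82, because the plan's calculation fixes the number of discordant pairs at 53 while the table lets it vary. No form of the test at 366 pairs exceeds 0.56.

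**4. What 366 pairs can show.**
- *Detectable effect.* For 5% against 1.25%, the discordant cells are 0.05 × 0.9875 = 0.049375 and 0.0125 × 0.95 = 0.011875. Exact two-sided power is 0.806. So 80% power needs a reduction of about 75%, not 50%.
- *Precision.* The standard error of the paired difference is √((0.0725 − 0.025²)/366) = 0.0140. The 95% half-width is 1.96 × 0.0140 = 0.027, or 2.7 percentage points, against a target difference of 2.5 points.
- *Attrition.* Lack of post-procedure follow-up is a removal criterion in Study Procedures, item g, but section 6c makes no allowance for it. If 10% of pairs were lost (an assumed figure), exact two-sided power would be 0.31.

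**The case against.** The unit error itself has no good defence. The phrase about 366 participants per condition cannot mean 732 patients, because the site targets add to 366. Counting several lesion levels per side does not help either, because section 6c says that a two-level bilateral ablation still yields two samples. Four points about the size of the error deserve a hearing.

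- *The plan does not state sidedness or test form.* This is true: the one-sided level is inferred from the reproduction, and the study hypothesis is directional in tone. The figure 0.35 combines the more conservative choice on both counts. With a one-sided asymptotic test, power would be about 0.55, and a significant result would be slightly more likely than not. Wording that looks for a difference at p < 0.05 ordinarily means two-sided, and no combination comes near 0.82.
- *A patient's two sides may be correlated.* Positive correlation lowers discordance and raises power. Keeping 5% and 2.5% and assuming discordance of 0.06, 0.04 or 0.03, exact power at 366 pairs is 0.42, 0.61 or 0.78 two-sided and 0.56, 0.73 or 0.86 one-sided. The confidence interval narrows too, to a half-width of about 2.5 points at 0.06 and 2.0 at 0.04. This limits how firmly 0.35 can be taken as a forecast. It does not rescue 0.82, which rests on the plan's own 0.0725.
- *The baseline may be higher than 5%.* The Background section gives 0.5% to 9.2% per lesion, and about 19% for cervical procedures. A halving from 9.2%, with independent sides, has exact power of 0.65 two-sided and 0.76 one-sided. A baseline below 5% gives less than 0.35. The plan chose 5%, and its stated power must follow from that.
- *Rewording does not restore power.* This stands. Correcting the text makes the claim true but leaves a trial with low power for its stated target.

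**Conclusion.** The concern holds, and the power statement in section 6c is wrong as written. The 732 is a number of pairs at a one-sided 0.05 level, and the plan enrols half that many pairs. On the plan's own inputs (5% against 2.5%, discordance 0.0725, independent sides, no attrition), exact McNemar power is 0.35 two-sided and 0.49 one-sided. If dexamethasone truly halves PAN, the two-sided exact test would miss it in about two trials out of three. Even 732 pairs would give only about 0.68 (exact) to 0.71 (normal approximation) two-sided.

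The pairs-for-sides error does not depend on the inference about sidedness. The exact size of the shortfall does depend on the test form, the within-patient correlation and the baseline rate.

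**What to change.** Rewrite the sample-size text in section 6c so that it:

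- says that 366 enrolled patients are 366 pairs, with about 26.5 discordant pairs expected under the stated assumptions;
- declares the sidedness and form of the test. A two-sided exact McNemar test at 0.05 fits the current wording; if another form is chosen, the power should be restated for it;
- replaces the stated power of 0.82 with about 0.35 for 5% against 2.5% under that test, and names the independence of the two sides as an assumption;
- gives the effect detectable with 80% power at 366 pairs, a fall from 5% to about 1.25%;
- commits to reporting the paired difference in incidence with its 95% confidence interval, and to describing a non-significant result as inconclusive rather than negative.

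This costs only text, at the price of a much less favourable power figure. It needs no extra patients or procedures. If the sponsor wants 80% power for a halving of PAN, that is a separate decision about enrolment: on the plan's inputs it takes 897 pairs two-sided by the method that reproduces the plan's figures, or 960 when the number of discordant pairs is allowed to vary.

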### 2. Objectives (include all primary and secondary objectives)

- Primary: To determine if the immediate administration of dexamethasone to the post-ablation site diminishes the incidence of post-ablation neuropathic pain
- Secondary: Stratify cervical vs. thoracic vs. lumbosacral data points to compare if post-ablation neuritis is dictated by anatomical location. Also look at the gauge of the needle used in each patient and radiofrequency parameters to see if associated with neuritis incidence. We will track level of disability and effectiveness of ablations with completion of Oswetry Disability Index and/or Neck Disability Index at baseline, 4 weeks, and 8 weeks after completion of bilateral ablations.

**3. Background** (briefly describe pre-clinical and clinical data, current experience with procedures, drug or device, and any other relevant information to justify the research)

Chronic neck and back pain has become one of the leading causes of disability and loss of productivity. This is often associated with poor quality of life, depression, anxiety, and sleep disorders. Conservative measures, such as physical therapy and medications are first-line treatment options and provide improvement of pain in some patients. However, for those who are not responsive to conservative management, interventional procedures are another treatment option. For many patients with facet- or sacroiliac joint-mediated pain who have responded to diagnostic nerve blocks, radiofrequency ablation of the nerve innervating the joints can provide long-term relief. Radiofrequency ablation (RFA) is a relatively safe procedure with minimal risk of adverse events.[1] However, with any procedure involving damage to the peripheral nervous system, there is risk of post-procedure neuropathic pain. Following both lumbar facet joint RFA, and sacroiliac joint RFA, PAN has been documented at a rate ranging from 0.5% to 9.2% per lesion. [2]

PAN is described as a burning pain at the level of the ablation. In patients who have undergone lumbar facet or sacroiliac joint radiofrequency denervation, these symptoms can last anywhere from 2 to 6 weeks. [2,3] Unfortunately, the incidence of PAN is higher in patients who have undergone cervical facet radiofrequency innervation. The incidence is reported to be approximately 19 percent, with an average duration of 2.6 months [4] and can drastically affect a patient's quality of life during this time period.

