## 7. Risks

- a. Medical risks, listing all procedures, their major and minor risks and expected frequency.
  - Radiofrequency ablation of cervical, lumbar, or thoracic facets or sacroiliac joint

- major risks: dural puncture, spinal cord injury, hematoma formation, infection. These are exceedingly rare with no cases reported in the literature to date. [5]
- minor risks: pain at injection site (0.5% frequency), and neuritis (0.5% to 19%), vasovagal reaction (1%)[3,6]
- Administration of steroids at the lesion site
  - major risks: infection, spinal cord injury are exceedingly rare. Reports are limited to a few case studies. In a large study by El-Yahchouchi et al. in 2016, showed with no reported incidences.
  - minor risks: flushing, headaches (2.6%). [7], increased blood glucose
- b. Steps taken to minimize the risks.
  - the procedure will be performed in a sterile fashion under fluoroscopic guidance to decrease the risk of infection, spinal cord injury, and dural puncture. Patients who are anticoagulated will not undergo the procedure. Only non-particulate steroids, such as dexamethasone, will be used to decrease the risk of spinal cord injury.
- c. Plan for reporting unanticipated problems or study deviations.
  - any unanticipated problems or study deviations will be reported immediately to the PI, who will then notify the IRB. Enrollment in the study will be stopped at that point until adjustments to the protocol can be made.
- d. Legal risks such as the risks that would be associated with breach of confidentiality.
  - As the proposed study does not involve collection or usage of information regarding sensitive materials, such as alcohol or drug use, illegal activities, sexual activity, or mental illness, potential breach of confidentiality does not pose large legal or societal risks. Patients will be de-identified through the assignment of subject ID numbers. The study team will take strong precautions to prevent any possibility of such breach by storing all data on encrypted servers and storing all hard copies of patient sensitive materials in the PIs' offices
- e. Financial risks to the participants: none

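### The 10% stopping limit in 6d is called greater than expected, yet it lies below the cervical rate the protocol reports, and it is read on the steroid side alone

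*Combined protocol and SAP*

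**What the plan says.** Section 6d (Early stopping rules) reads: "study will also be terminated if there appears to be greater than expected (>10%) incidence of PAN in the treatment group during interim analyses". It gives no derivation of the 10%, no denominator, and no number or timing of looks. It does not mention the saline side or the spinal region.

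The other rates in the document are:

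- **6c:** a baseline incidence of 5% and a steroid-side incidence of 2.5%, with one sample per treated side and each patient giving one steroid side and one saline side.
- **Section 3 (Background), lumbar and sacroiliac:** "PAN has been documented at a rate ranging from 0.5% to 9.2% per lesion".
- **Section 3, cervical:** "the incidence of PAN is higher in patients who have undergone cervical facet radiofrequency innervation", and "The incidence is reported to be approximately 19 percent, with an average duration of 2.6 months". The cited source (reference 4) is titled as a study of third occipital nerve denervation.
- **7a (Medical risks):** neuritis after ablation at 0.5% to 19%, in answer to a form prompt that asks for "listing all procedures, their major and minor risks and expected frequency".

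Section 4 admits "patients with a diagnosis of either cervical, thoracic, or lumbar facet or sacroiliac joint pain" and gives no cap or expected share by region. Section 2 has a secondary aim to "Stratify cervical vs. thoracic vs. lumbosacral data points to compare if post-ablation neuritis is dictated by anatomical location", so a mixed sample is intended.

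**The concern.** The rule describes its limit as a departure from expectation, but the document holds several expectations and 10% exceeds only some of them. It is well above the pooled planning rates. It is not above what section 3 reports for cervical patients, whom the trial recruits.

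The rule also reads one side only. A steroid-side rate above 10% could mean that the steroid does harm, or that many cervical patients were enrolled and the steroid does nothing. The paired saline side, already collected in the same patients, would separate the two explanations, but 6d does not use it. Followed as written, the rule can end the trial, and have it reported as excess PAN in the treatment group, when PAN is at its background rate.

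**Working it through.** **Planning rates.** The 10% has no stated derivation to reproduce. The 5% and 2.5% can be checked against 6c. With independent sides, the discordant probability is 0.05 × 0.975 + 0.025 × 0.95 = 0.04875 + 0.02375 = 0.0725, and the odds ratio is 0.02375 / 0.04875 = 0.487. Both match 6c, so 2.5% is the planned steroid-side rate and 10% is four times that rate.

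**Where 10% sits.** Let f be the cervical share and q the rate in other regions. With no steroid effect, the expected steroid-side incidence is 0.19f + q(1 − f). It equals 10% when f = (0.10 − q) / (0.19 − q):

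- q = 0.05 (6c): 0.05 / 0.14 = 36%
- q = 0.092 (top of the section 3 range): 0.008 / 0.098 = 8%
- q = 0.005 (bottom of that range): 0.095 / 0.185 = 51%

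The last two treat a per-lesion rate as a per-side rate, which is an assumption.

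**Chance of crossing.** Assume the incidence is counted per side (the unit of 6c) and that there is one look at half the 366 patients, n = 183. The rule fires at 19 or more affected steroid sides (19/183 = 10.4%; 18/183 = 9.8%). The probability is exact, from the sum of two binomials, one for cervical patients and one for the rest. The scenarios are:

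- **A:** no effect; 19% per cervical side, 5% elsewhere.
- **B:** no effect; the 19% is per bilaterally treated patient. With independent sides the per-side rate is 1 − √(1 − 0.19) = 10.0%; 5% elsewhere.
- **C:** the steroid halves PAN; 9.5% cervical, 2.5% elsewhere.

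| Cervical share | Expected rate, A | Fires, A | Fires, B | Fires, C |
|---|---|---|---|---|
| 0 | 5.0% | 0.2% | 0.2% | <0.1% |
| 20% | 7.8% | 12% | 1.4% | <0.1% |
| one third | 9.7% | 41% | 4% | 0.1% |
| half | 12.0% | 79% | 9% | 1.4% |
| all | 19.0% | >99% | 47% | 38% |

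**Sensitivity.**

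- *Look size, scenario A:* at n = 100 the chances are 1%, 15%, 37% and 67% for shares of 0, 20%, one third and half. At n = 50 they are 4%, 19%, 36% and 57%.
- *Rate elsewhere:* with 2.5% elsewhere, no effect and n = 183, the chances are 0.8%, 14% and 61% at shares of 20%, one third and half.
- *Repeated looks:* under scenario A with looks at 92, 183 and 275 patients, simulation gives roughly 25%, 59% and 91% for those three shares. No such schedule is in the protocol.
- *Denominator:* suppose incidence were counted per lesion, with two lesions per side and at most one recorded as affected. Crossing would then need 37 of 366 lesions, that is 37 of 183 sides (20.2%). Scenario A would give below 0.01% at one third cervical and 0.08% at half. The unstated denominator alone therefore decides whether the rule is sensitive or nearly inert.

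**The case against.** The limit applies to the treatment group, and the only rate the document plans for that group is 2.5%. Against that figure 10% is a generous ceiling. The 19% is for ablation without study steroid. An absolute ceiling on the treated side also fits the protocol's definition of treatment failure, which is PAN within two months of the steroid injection. If the steroid works as hoped, the rule rarely fires at a mixed-region share. If it fires because the steroid does nothing, the trial lost is one of an ineffective treatment.

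Much of this stands. A reader might infer that the protocol expects 19% PAN in this trial. It does not go that far: the phrase about expected frequency is the form's prompt, section 3 speaks of a reported incidence, and the cited title concerns one cervical nerve. A reader might also infer that the rule is likely to stop a trial in which the steroid works. Scenario C does not support that: 0.1% at one third cervical, 1.4% at half, and 38% only if every patient is cervical, while section 4 admits four regions.

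What the objection does not answer is that 6d words its limit as an excess over expectation, not as an absolute ceiling, and the document's own figures disagree on what is expected. A stopping rule must also behave sensibly when the drug has no effect, and there this one cannot tell background from harm.

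**Conclusion.** The concern holds as an inconsistency in a stated decision rule. The conflict between 6d, section 3 and 7a, and the single-side reading, are on the page and need no assumption. The size does. The chance of a stop under no effect runs from 0.2% with no cervical patients to 79% at half cervical, on 19% per cervical side, 5% elsewhere, per-side counting and one look at 183. It is about 4% to 9% at one third to half cervical if the 19% is per patient. Region mix, look timing, denominator and the unit of the 19% are all assumed because the protocol does not give them.

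The documents do not show that the rule will fire, that an effective steroid is likely to be stopped, or that the McNemar test is invalid; none of these is claimed. This should be corrected before the first interim look.

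**What to change.** In 6d:

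1. Reconcile the 10% and its description as beyond expectation with the 5% and 2.5% in 6c, the two ranges in section 3 and the range in 7a. State the expected rate by region and the expected cervical share. If an absolute ceiling is meant, say so.
2. Define the incidence as steroid-treated sides with any PAN divided by steroid-treated sides followed, which is the unit of 6c.
3. At each look, read that incidence against the saline-side incidence in the same patients, and report both.
4. State the number and timing of looks, and the chance of crossing at the expected rate for the expected region mix.

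The sponsor sets the threshold; none is proposed here.

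The cost is a short paragraph and one calculation, with no change to sample size, visits or the final test. The existing rule already requires someone to know which side received steroid, so tabulating the saline side adds little. The trade-off is that the rule is no longer a simple single-side ceiling.
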